In Study LX4211.1 202 DM (40) sotagliflozin induced a dose-dependent increase of hematocrit, albumin, and hemoglobin. The mean change (standard deviation [SD]) in hematocrit from Baseline to Week 12 was 0.9% (2.52), 2.0% (2.47), and 1.9% (2.78) in patients receiving sotagliflozin 200 mg qd, 200 mg bid and 400 mg qd, respectively versus -0.5 (2.98) % in the placebo arm. The mean change (SD) in albumin from Baseline to Week 12 was 0.0 (0.279), 0.09 (0.243) and 0.12 (0.242) g/dL in patients receiving sotagliflozin 200 mg qd, 200 mg bid and 400 mg qd, respectively versus (0.273) -0.04 g/dL in the placebo arm. The mean change (SD) in hemoglobin from Baseline to Week 12 was 0.29 (0.775), 0.55 (0.688) and 0.60 (0.820) g/dL in patients receiving sotagliflozin 200 mg qd, 200 mg bid and 400 mg qd, respectively versus -0.19 (1.084) g/dL in the placebo arm. In addition, in the same study, a prespecified sub-analysis of patients with a Baseline BP  $\geq$ 130 mmHg showed that systolic BP decreased by 7 and 14 mmHg (placebo-subtracted), respectively, in the 200 mg qd and 400 mg qd groups.

Therefore, given the observed higher efficacy of the 400 mg dose on glycemic control, hemoconcentration, and BP reduction, and given the potential benefit of these changes on cardiovascular outcomes, the dose of 400 mg was chosen as the proposed maintenance dose for the study.

Sotagliflozin induces an acute, but modest, decrease in estimated glomerular filtration rate (eGFR). Since the study population includes patients at increased risk of acute kidney injury (ie, patients with moderately impaired renal function), study treatment will begin with the low dose of sotagliflozin (200 mg qd) and will be increased to the maintenance dose of 400 mg qd, once tolerability of the low dose has been established by the Investigator.

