## 2 STATISTICAL AND ANALYTICAL PROCEDURES

### 2.1 ANALYSIS ENDPOINTS

#### 2.1.1 Demographic and baseline characteristics

Baseline eGFR, hemoglobin A1c (HbA1c), and other laboratory parameter values for each patient are defined as the value assessed by the central laboratory at randomization.

For the remaining parameters, baseline is defined as the last available value before the first dose of double-blind investigational medicinal product (IMP) or the last available value on or before the day of randomization for patients who were randomized but never exposed to IMP.

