### ***2.1.3.2 Secondary efficacy endpoints***

- Total occurrences (first and potentially subsequent) of HHF and urgent HF visits
- Time from randomization to occurrence of CV death
- Total occurrences (first and potentially subsequent) of CV death, HHF, non-fatal myocardial infarction, and non-fatal stroke
- Total occurrences (first and potentially subsequent) of HHF, urgent HF visit, CV death, and HF while hospitalized
- Time from randomization to all-cause mortality
- Change in KCCQ-12 scores from baseline to Month 4
- Rate of decline in eGFR after Week 4 (mL/min/1.73m^2/year) to the end of the study

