#### ***2.4.4.2 Analyses of secondary efficacy endpoints***

Methods for controlling the overall type-I error rate when testing the secondary efficacy endpoints are described in Section 2.4.4.3 *Multiplicity issues*.

Time-to-event secondary efficacy endpoints will be analyzed using the same statistical methodology as for the primary endpoint. Deaths that are not part of a given endpoint will be treated as competing events.

As with the primary endpoint, the absolute risk reduction (ARR) of time-to-event secondary endpoints will be estimated by the difference between treatment groups in the number of events per 100 patient-years of follow-up. For those secondary endpoints which are a composite of events, results will be provided for both the overall composite and its individual components.

Absolute change in KCCQ-12 scores from baseline to Month 4 will be analyzed by analysis of covariance (ANCOVA) with treatment group as factor and baseline KCCQ-12 score and randomization stratification factors as covariates. The last available post-baseline score will be

carried forward to Month 4 if the patient is alive at Month 4 but the Month 4 value is missing. For patients who die, a worst score (0) will be imputed for the clinical summary score at all subsequent scheduled visits after the date of death where the clinical summary score would have been assessed.

The rate of decline in eGFR observed over time will be analyzed by repeated-measures mixed-effects models with absolute change in eGFR from baseline as the outcome, a random effect for intercept, and fixed effects for treatment, baseline value, and time. An additional model will be developed with an interaction between treatment and time. The variance-covariance matrix will be specified to be unstructured.

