#### ***2.4.4.3 Multiplicity issues***

In order to handle multiple main secondary endpoints, the overall type-I error will be controlled by the use of a sequential inferential approach. Statistical significance of the primary endpoint is required before drawing inferential conclusions about first secondary endpoint at the 0.05 2-sided alpha level. Inferential conclusions about successive secondary endpoints require statistical significance of the prior one. The order of tests is detailed in Section 2.1.3.2 *Secondary efficacy endpoints*. This fixed hierarchical approach will ensure a strong control of the overall type-I error rate at the required 0.05 2-sided level.

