#### ***2.4.4.4 Additional efficacy analysis(es)***

Time-to-event other efficacy endpoints will be analyzed using the same statistical methodology as for the primary endpoint. If the endpoint concerns the first event, then only the first event experienced by a given patient will be included in the analysis. Deaths that are not part of a given endpoint will be treated as competing events.

For the analyses of DAOH and PDAOH, total potential follow-up time for each patient is defined as the number of days from date of randomization until the patient's date last known alive, or May 1, 2020 (the date sites were instructed to complete end of study contacts with patients; patients known to have died after this date will be censored as alive as of May 1, 2020) if the patient died. The total number of days spent in hospital will be derived from the investigator reports. If a patient died, the number of days dead will be calculated as the time interval between their date of death and May 1, 2020. DAOH will be calculated by subtracting days in hospital and days dead from total potential follow-up time; if a patient survived without hospitalization, DAOH will be equal to the potential follow-up time for that patient.

DAOH, days dead, and days in hospital will be compared between treatment groups by rate ratios (RRs) from a Poisson regression model with a log link function and Pearson  $\chi^2$  scaling of standard errors to account for potential overdispersion. In addition to treatment group, the logarithm of potential follow-up time will be used as an offset variable in the model. Given the expectation that a fraction of patients will survive without hospitalization until the end of follow-up (i.e., PDAOH =100%), PDAOH will be compared between treatment groups with one-inflated beta regression. In this application, the model will jointly estimate the treatment odds ratio (OR) of surviving until the end of the study without hospitalization (ie, PDAOH =100%), and the treatment OR of higher mean PDAOH among the subset of patients who died or had at least one hospitalization or died during follow-up (i.e., PDAOH <100%). Plots of the distribution of DAOH will be constructed,

as well as summaries of reasons for hospitalizations (e.g., HF, other efficacy event, non-efficacy adverse event, etc.).

Changes from baseline in NT-proBNP, hematocrit, HbA1c, body weight, and SBP will be analyzed using the same methods as for change in eGFR.

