### Appendix D Key Changes to Original Planned Analysis and Protocol

Change	Rationale
Primary endpoint analyzes total occurrences (first and potentially subsequent) rather than first occurrence	Total occurrences are expected to be a more sensitive indicator of treatment benefit, are clinically relevant to patients with heart failure, and have been sensitive to change in several cardiovascular outcomes trials
Primary endpoint adds urgent HF visit to original planned endpoint of CV mortality and HHF	Urgent HF visits are clinically relevant and can be reduced by effective treatment
All event endpoints based on investigator reporting rather than adjudication	Adjudication was not completed, and investigator-reported events are clinically relevant
Only one primary objective is applied to the overall population: initially there were co-primary objectives, one to demonstrate reductions in CV morbidity and mortality in those with LVEF<50%, and one to demonstrate reductions in CV morbidity and mortality in the overall population	Primary focus is on overall population rather than subgroups
Composite renal endpoint was moved from a secondary objective to other objective; change in eGFR over time was added as a secondary benefit	Given the current follow-up in SOLOIST, change in eGFR over time is a more sensitive measure of renal benefit than the composite renal endpoint
Addition of ARR, DAOH and PDAOH as other endpoints	ARR provides a perspective of treatment benefit, and DAOH and PDAOH capture clinical relevance of decreased hospitalizations
Hypoglycemia safety moved to efficacy endpoint	Reductions in hypoglycemia have been seen with sotagliflozin in both type 1 diabetes and T2D, indicating the value of statistical analyses of hypoglycemia results
CV death and HHF in patients with LVEF <50%, with and without T2D (a secondary endpoint in Amendment 2) is not included in current analysis plan	Limited enrollment after Amendment 2 means subgroup analysis of those without T2D is not adequately powered for a secondary endpoint
All-cause mortality was a secondary endpoint in the original protocol, moved to “other	Original move to “other endpoint” was based on FDA feedback that it would not be included

endpoint” in Protocol Amendment 2, and returned to a secondary endpoint in this analysis plan	in labeling, but it was returned to secondary endpoint because of its high clinical relevance

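### The eGFR slope endpoint leads with a model that cannot estimate a slope difference, and the treatment-by-time coefficient that can is not named as the hierarchical test

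*SAP*

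**What the plan says.** SAP 2.1.3.2 lists seven secondary endpoints. The seventh is the "Rate of decline in eGFR after Week 4", in mL/min/1.73m2 per year, to the end of the study. SAP 1.2.2 words the matching objective only as a change in eGFR.

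SAP 2.4.4.2 takes absolute change from baseline as the outcome. The only random term it lists is for the intercept. For the rest of the model it specifies "fixed effects for treatment, baseline value, and time. An additional model will be developed with an interaction between treatment and time". It then says that the variance-covariance matrix will be unstructured, without saying which matrix.

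Baseline eGFR is "defined as the value assessed by the central laboratory at randomization" (SAP 2.1.1), that is, before any effect of study drug. Protocol 4.4.1 states: "Sotagliflozin induces an acute, but modest, decrease in estimated glomerular filtration rate (eGFR". It gives no size.

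SAP 2.4.4.3 sets a fixed order at two-sided 0.05: "Inferential conclusions about successive secondary endpoints require statistical significance of the prior one". It names neither a model nor a coefficient for the eGFR endpoint. SAP Appendix D moves the composite renal endpoint out of the secondary set because "change in eGFR over time is a more sensitive measure of renal benefit than the composite renal endpoint".

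**The concern.** The endpoint is a slope, so the between-arm comparison should be a difference in slopes. A model with treatment, baseline value and time, and no treatment-by-time term, gives both arms the same fitted slope. Its treatment coefficient answers another question: how far apart the arms lie on average after randomization. An acute haemodynamic decrease on sotagliflozin enters that coefficient directly.

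The model that does estimate a slope difference is introduced second and called additional. Two candidate coefficients are therefore available for one confirmatory test, and they can point in opposite directions. Following the lead model as written could hide a real slowing of decline or report it as harm. This matters for interpretation because Appendix D relies on eGFR over time as the main renal measure.

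**Working it through.** The documents give no sample size, SD, slope difference or power for this endpoint, so there is no figure of the plan's own to reproduce. The check is algebra first, then illustration.

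**Inputs from the documents.** Endpoint and units (SAP 2.1.3.2); model terms (SAP 2.4.4.2); pre-dose baseline (SAP 2.1.1); an acute decrease of unstated size (Protocol 4.4.1); visits at Day 29, Day 113 and every 4 months thereafter (Protocol 1.2); enrollment closed in March 2020 (SAP 1.1) and end-of-study contacts from May 1, 2020 (SAP 2.4.4.4), which puts the shortest follow-up at roughly 1.5 months.

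**Assumed.** Dip of 0 to 2; true slope benefit of 0 or +2 per year; 300, 600 or 1000 patients per arm; residual/intercept/slope SDs of 6/5/4 or 8/8/6; longest follow-up 21 months.

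**Step 1, algebra.** Let D be the acute shift on sotagliflozin and S the true slope difference.

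- Model A: change = b0 + b1·trt + b2·baseline + b3·time + random intercept. The slope difference is 0 by construction.
- Model B: Model A + b4·trt·time. The slope difference is b4.
- Fitted to the same data, Model A's b1 estimates D + S × (mean visit time). Model B's b4 estimates S.

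This step does not depend on the assumed SDs when visits are balanced.

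**Step 2, sign.** For visits at days 29, 113, 243 and 365, the mean time is (750/4)/365.25 = 0.513 year. With D = -2 and S = +2, b1 = -2 + 2 × 0.513 = -0.97. With visits at Weeks 4, 16, 32, 48, 64 and 80 and follow-up spread over 1.5 to 21 months, the effective mean time is about 0.45 year, so b1 = -2 + 2 × 0.45 = -1.1. In both designs b4 averages about +2.

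The sign of b1 is wrong whenever S is below |D| / mean time. For D = -2 that threshold is 2/0.513 = 3.9 to 2/0.45 = 4.4 per year.

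**Step 3, test results.** 500 simulated trials per scenario in the second design, Monte Carlo error at most about 2 points. Ranges run over the two SD sets.

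| Truth and coefficient | 300 per arm | 600 | 1000 |
|---|---|---|---|
| Equal slopes, dip 1: b1 significant against sotagliflozin | 26-48% | 41-77% | 64-94% |
| Equal slopes, dip 2: b1 significant against sotagliflozin | 73-96% | 95-100% | 100% |
| Benefit +2, dip 2: b1 significant against sotagliflozin | 24-57% | 47-82% | 72-95% |
| Benefit +2, dip 2: b4 significant in favour (random slope fitted) | 42-68% | 67-92% | 87-100% |

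With no dip and equal slopes, b1 rejects in 4-7%. In the simpler four-visit design with equal slopes, a dip of 2 and 600 per arm, b1 rejects in 95% and b4 in about 4%. The b1 rejections are real level differences. They mislead only if read as a slope result.

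**Step 4, covariance.** A single random intercept has a 1×1 matrix, for which *unstructured* has no content. The sentence must refer either to the residual covariance across visits or to a set of random effects that the SAP does not list.

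- *Residual visit covariance.* Variation in patients' slopes is absorbed. At 300 per arm with equal slopes, the interaction test rejected in 6.0% under both SD sets (Monte Carlo error about 1 point). Power for +2 per year was 67% and 41%, against 68% and 42% with a random slope.
- *Random intercept with independent residuals.* The standard error of b4 is too small when slopes vary. For SDs 6/5/4 at 300 per arm it averages 0.71, against 0.83 with a random slope. The ratio implies rejection of about 2Φ(-1.96 × 0.71/0.83) = 9%. Over assumed slope SDs of 2 to 6 the range is about 6-11%, against a nominal 5%.

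**The case against.** The best defence is that the slope analysis is already there. SAP 2.4.4.2 places both models under the rate of decline and commits to the interaction model. The units in SAP 2.1.3.2 fit only the interaction coefficient in a between-arm comparison. The additive model also has a use, since the objective in SAP 1.2.2 speaks only of change. This stands: a slope difference will be estimated, and what is missing is its designation as the test.

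The defence on impact also stands. The endpoint is reached only after the primary and six earlier secondaries are significant, in a trial that SAP 1.3 says is not powered for its original assumptions, and no test follows it.

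Three stronger readings are tempting, and the documents do not support them.

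- A reader might infer that SAP 2.4.4.4 settles the matter in favour of a level difference, because changes in NT-proBNP, hematocrit, HbA1c, body weight and SBP "will be analyzed using the same methods as for change in eGFR". The plural covers both models, and those endpoints lie outside the hierarchy.
- A reader might infer that the slope test certainly has an inflated error rate because no random slope is listed. That follows only if the sentence on an unstructured matrix does not mean the residual visit covariance.
- A reader might infer a risk of a false renal benefit from the additive model. An acute decrease pushes its treatment term the other way.

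**Conclusion.** The point holds as a gap in the definition of one confirmatory test, and it should be fixed. The lead model cannot estimate the stated endpoint, and its treatment term mixes the acute decrease with the slope effect. That part is algebra. The wrong-sign example (about -1.1 for a true +2 per year) assumes a dip of 2, where the protocol says only that the decrease is modest. The rejection rates also rest on assumed SDs, arm sizes and follow-up. They show direction and possible size and do not predict this trial's result.

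The likely harm is a masked or wrong-direction renal finding. The error-rate question about the random intercept is conditional on what *unstructured* refers to, and the SAP should say so.

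**What to change.** In SAP 2.4.4.2, state that:

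- the hierarchical test is the treatment-by-time coefficient, two-sided 0.05, reported with its confidence interval;
- time is continuous, in years;
- the data are central-laboratory eGFR values in the post-Week-4 period of SAP 2.1.3.2, with an explicit statement on whether the Week 4 visit itself is included;
- the model without the interaction is descriptive.

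Also state which matrix is unstructured. If it is the residual visit covariance, no random slope is needed. If the model is a random intercept with independent residuals, add a random slope with an unstructured 2×2 covariance and declare it as a model change. Naming the model for the non-hierarchical changes in SAP 2.4.4.4 is optional.

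**Cost.** No new data. Naming the coefficient is a wording change. A random slope, if needed, lowers nominal power modestly: for +2 per year and SDs 6/5/4, from 77% to 68% at 300 per arm and from 95% to 92% at 600.

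Two limitations should be stated. Power for a smaller benefit is low: with the random slope, +1 per year is detected in 14-21%, 22-45% and 38-61% at 300, 600 and 1000 per arm. And Protocol 8.1.1.1 allows up-titration as late as Month 8, so some acute change may fall after Week 4 and enter the slope.

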#### ***2.4.4.3 Multiplicity issues***

In order to handle multiple main secondary endpoints, the overall type-I error will be controlled by the use of a sequential inferential approach. Statistical significance of the primary endpoint is required before drawing inferential conclusions about first secondary endpoint at the 0.05 2-sided alpha level. Inferential conclusions about successive secondary endpoints require statistical significance of the prior one. The order of tests is detailed in Section 2.1.3.2 *Secondary efficacy endpoints*. This fixed hierarchical approach will ensure a strong control of the overall type-I error rate at the required 0.05 2-sided level.

#### ***2.4.4.4 Additional efficacy analysis(es)***

Time-to-event other efficacy endpoints will be analyzed using the same statistical methodology as for the primary endpoint. If the endpoint concerns the first event, then only the first event experienced by a given patient will be included in the analysis. Deaths that are not part of a given endpoint will be treated as competing events.

For the analyses of DAOH and PDAOH, total potential follow-up time for each patient is defined as the number of days from date of randomization until the patient's date last known alive, or May 1, 2020 (the date sites were instructed to complete end of study contacts with patients; patients known to have died after this date will be censored as alive as of May 1, 2020) if the patient died. The total number of days spent in hospital will be derived from the investigator reports. If a patient died, the number of days dead will be calculated as the time interval between their date of death and May 1, 2020. DAOH will be calculated by subtracting days in hospital and days dead from total potential follow-up time; if a patient survived without hospitalization, DAOH will be equal to the potential follow-up time for that patient.

DAOH, days dead, and days in hospital will be compared between treatment groups by rate ratios (RRs) from a Poisson regression model with a log link function and Pearson  $\chi^2$  scaling of standard errors to account for potential overdispersion. In addition to treatment group, the logarithm of potential follow-up time will be used as an offset variable in the model. Given the expectation that a fraction of patients will survive without hospitalization until the end of follow-up (i.e., PDAOH =100%), PDAOH will be compared between treatment groups with one-inflated beta regression. In this application, the model will jointly estimate the treatment odds ratio (OR) of surviving until the end of the study without hospitalization (ie, PDAOH =100%), and the treatment OR of higher mean PDAOH among the subset of patients who died or had at least one hospitalization or died during follow-up (i.e., PDAOH <100%). Plots of the distribution of DAOH will be constructed,

as well as summaries of reasons for hospitalizations (e.g., HF, other efficacy event, non-efficacy adverse event, etc.).

Changes from baseline in NT-proBNP, hematocrit, HbA1c, body weight, and SBP will be analyzed using the same methods as for change in eGFR.

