# 1 OVERVIEW AND INVESTIGATIONAL PLAN

## 1.1 BACKGROUND

SOLOIST is a Phase 3, multicenter, randomized, double-blind, placebo-controlled, parallel group, stratified study of sotagliflozin for the treatment of patients with worsening heart failure.

After screening, patients who met all eligibility criteria were centrally randomized via in a 1:1 ratio to sotagliflozin or placebo at randomization visit. Randomization was stratified by baseline left ventricular ejection fraction (LVEF) (LVEF<50% and LVEF≥50%) and region (North America, Latin America, Western Europe, Eastern Europe, and rest of the world).

The original plan was to randomize approximately 4000 patients. However, SOLOIST enrollment was closed in March 2020 before meeting this objective.

A recent publication in the Journal of the American College of Cardiology discussed how clinical trials and programs have been disrupted by the COVID-19 pandemic. It provided the sotagliflozin program as an example where clinical trials have been prematurely terminated. Recommendations included careful consideration of statistical issues relating to potential loss of power, increased variability in data, and challenges in adjudication of events. Similarly, the FDA has issued guidance specific to COVID-19 recognizing the potential for disruption of clinical trials and identifying some of the data and statistical issues that need to be addressed by investigators and sponsors.

This plan describes statistical efficacy analyses to be conducted by an independent academic statistician and separately verified by the Lexicon statistical team. It addresses issues related to the early termination of SOLOIST. These issues have been reviewed and the recommended steps have been chosen in a blinded fashion without the use of any unblinded interim analysis.

The termination of enrollment and follow-up of SOLOIST did not allow enough time to amend the study protocol. Changes to the intended analysis plan are reflected in this document, rather than the protocol, and this plan takes precedence where there are differences between the two documents.

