### ***2.1.3.3 Other efficacy endpoints***

- First occurrence of CV death, HHF, or urgent visit for HF
- First occurrence of CV death or HHF
- Total occurrences (first and potentially subsequent) of HHF after randomization
- Total occurrences (first and potentially subsequent) of urgent HF visits after randomization
- First occurrence of CV death, HHF, urgent visit for HF, non-fatal myocardial infarction, and non-fatal stroke
- First occurrence of fatal and non-fatal MI
- First occurrence of fatal and non-fatal stroke
- First occurrence of new onset of atrial fibrillation or atrial flutter (adverse events (AEs) with a preferred terms (PTs) of atrial fibrillation or atrial flutter)
- First occurrence of a composite renal endpoint, consisting of events sustained  $\geq 50\%$  decrease in eGFR from baseline (for  $\geq 30$  days), chronic dialysis, renal transplant, or sustained eGFR  $< 15$  mL/min/1.73m^2 (for  $\geq 30$  days)
- First occurrence of severe hypoglycemia
- Total occurrences of the following hypoglycemia categories
  - Severe hypoglycemia
  - Hypoglycemia with documented glucose value  $< 54$  mg/dL
  - Hypoglycemia with documented glucose value  $< 70$  mg/dL
- Days alive and out of hospital (DAOH) and percent DAOH (PDAOH)

- Changes from baseline in NT-proBNP, hematocrit, HbA1c, body weight, and SBP

All time-to-event endpoints are assessed based on investigator-reported events.

Cardiovascular death includes death of undetermined cause.

The first occurrence of the composite renal endpoint is defined as follows:

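### DAOH and PDAOH follow-up ends on 1 May 2020 for patients who died but at an uncapped last-alive date for survivors, so the denominator depends on the outcome

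*SAP*

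**What the plan says.** SAP section 2.4.4.4 defines potential follow-up as the days from randomization "until the patient's date last known alive, or May 1, 2020". The bracket that follows, and the condition that closes it, decide who gets which date: "patients known to have died after this date will be censored as alive as of May 1, 2020) if the patient died". So there are two rules.

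- **Patient who died:** the end date is 1 May 2020. Time dead is filled in up to it: "the number of days dead will be calculated as the time interval between their date of death and May 1, 2020". A death after that date is truncated there.
- **Survivor:** the end date is the date last known alive, with no cap at 1 May and no extension to it.

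For survivors the section adds that "if a patient survived without hospitalization, DAOH will be equal to the potential follow-up time for that patient", which makes PDAOH 100% however short the follow-up. In the Poisson models for DAOH, days dead and days in hospital, "the logarithm of potential follow-up time will be used as an offset variable in the model". The one-inflated beta model for PDAOH then treats a value of 100% as having lived to study end with no hospital stay.

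SAP section 2.1.3.3 lists DAOH and PDAOH among the other efficacy endpoints, and the fixed sequence in section 2.4.4.3 does not include them. No sensitivity analysis of the end date is specified.

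**The concern.** An offset or a percentage denominator should be the time a patient could have contributed, fixed without reference to what happened. Here the end date is chosen by vital status, so two patients randomized on the same day can have different potential follow-up only because one of them died.

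The mismatch runs in both directions. Survivor time after 1 May enters the numerator and the denominator, while no patient who died can contribute any. Before 1 May, a survivor who is lost stops counting at last contact, while a patient who died keeps counting to 1 May.

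At stake is the interpretation of the reported levels (share of time dead, mean PDAOH, proportion at 100%). If last-contact dates differ between arms, the comparison is affected too. That is possible: under protocol sections 6.1.3 and 6.2.2, patients still on study drug have a final visit 14 ± 4 days after close-out, while those who stopped early finish at close-out. Last-alive dates may therefore follow treatment discontinuation.

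**Working it through.** The SAP states no numerical DAOH result, so there is no figure to reproduce. The check has three steps.

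**1. Worked example from the definition.** Randomization is on 1 May 2019, with no hospital days. The interval to 1 May 2020 is 366 days.

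| Patient | Potential follow-up | DAOH | PDAOH |
|---|---|---|---|
| Died on day 200 | 366 | 200 | 200/366 = 54.6% |
| Lost alive on day 200 | 200 | 200 | 100% |
| Alive at contact on 31 May 2020 | 366 + 30 = 396 | 396 | 100% |
| Died on 30 May 2020 (truncated) | 366 | 366 | 100% |

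The first two were observed for the same time. The last two were both alive on 1 May. In each pair the denominators differ only through the outcome.

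The relative difference is largest for late entrants, since "SOLOIST enrollment was closed in March 2020 before meeting this objective". A patient randomized on 31 March 2020 has 31 days to 1 May. A survivor contact on 31 May makes that 61.

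**2. Survivors contacted after 1 May.** Assumptions not in the documents: entry spread evenly over 1.5 to 22 months before 1 May 2020, placebo mortality 16 per 100 patient-years, mortality hazard ratio 0.81 (the protocol's planning value for its primary composite, borrowed here), no hospital days, and every survivor contacted the same number of days after 1 May.

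Share of time dead = total days dead / total potential follow-up.

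- With everyone capped at 1 May, simulation gives 9.2% in the placebo arm.
- With uncapped survivors contacted 14 to 60 days later, it gives 8.9% to 8.1%.
- The DAOH ratio moves by at most about 0.002.

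Hand check: mean time to 1 May is 11.75 months, about 358 days, so days dead per patient are 0.092 × 358 = 32.9. If about 86% survive, 14 extra days give 32.9 / (358 + 0.86 × 14) = 32.9 / 370.0 = 8.9%. Sixty extra days give 32.9 / (358 + 0.86 × 60) = 32.9 / 409.6 = 8.0%, close to the simulated value.

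**3. Survivors last known alive before 1 May.** A cap changes nothing here, because their follow-up already ends before it. Assumptions: mortality 15% per year, equal in both arms; entry 47 to 687 days before 1 May; other survivors last seen exactly on 1 May; deaths after loss found through vital-status checks. The only loss figure in the documents is the 2% annual censoring assumed in protocol section 11.1.

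| Annual loss, arm A / arm B | Share dead under SAP rule, A / B | Days-dead ratio (B/A) | Share dead and ratio, common end date |
|---|---|---|---|
| 2% / 2% | 8.90% / 8.90% | 1.000 | 8.81%, 1.000 |
| 10% / 10% | 9.26% / 9.26% | 1.000 | 8.81%, 1.000 |
| 2% / 10% | 8.90% / 9.26% | 1.040 | 8.81%, 1.000 |

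In the last row the alive-days ratio is 0.996.

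The common-date column depends on finding deaths after loss. If they are not found, and lost patients are simply counted as alive to 1 May, the 2% / 10% case gives a days-dead ratio of 0.965, against 1.010 under the SAP rule. Extending lost patients as alive is therefore not a neutral remedy.

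**The case against.** The case for leaving the rule alone is strong on weight.

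- **No confirmatory consequence.** DAOH and PDAOH are outside the hierarchy, so the primary and secondary tests are untouched.
- **Same rule in both arms.** With equal mortality and equal follow-up the ratio is 1.000 whatever the loss. What moves is the level.
- **Contacts may cluster near 1 May.** The SAP describes it as the date on which sites were told to complete end-of-study contacts. Whether that was a deadline or the date of the instruction is unclear, but shifts of 60 days are not documented.
- **Some asymmetry is unavoidable.** Time after death needs a conventional end date, and survivor time after last contact was not observed.

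All four stand. They make the point small but do not make the two end dates consistent.

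Two stronger readings are tempting. One is that the SAP hides deaths, because "patients known to have died after this date will be censored as alive as of May 1, 2020". It does not: a patient who died on 10 May was alive on 1 May, and truncating there is right. The inconsistency is that survivors are not truncated in the same way. The other is that the treatment comparison is biased. The documents give neither actual losses nor contact dates by arm, so nothing in them shows the differential follow-up that would be needed when there is no treatment effect.

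**Conclusion.** The point holds as a minor defect of definition. The DAOH offset and the PDAOH denominator depend on whether the patient died; this follows from the wording and needs no simulation.

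For contacts after 1 May the distortion is a level shift of about 0.3 to 1.1 percentage points in the placebo share of time dead (9.2% less 8.9% or 8.1%), with almost no change in the DAOH ratio. For patients lost before 1 May, the shift at the protocol's 2% planning rate is about 0.1 point (8.90% against 8.81%). A between-arm error of the order of 1.04 in days dead appears only with strongly unequal loss, which is an assumption here.

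A separate problem of description remains: a patient lost early with no hospital stay is placed in the PDAOH 100% group and read as having survived to study end, which was not observed.

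Every size above rests on assumed mortality, entry, loss and contact timing.

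**What to change.** 1. **Cap everyone.** Define potential follow-up as randomization to 1 May 2020, or to the date last known alive if that is earlier and the patient is not known to have died by 1 May. Ignore alive days and hospital days after 1 May for all patients. The existing truncation of later deaths already agrees with this and can stay.
2. **Report what the cap cannot reach.** By arm, give the number of survivors last known alive before 1 May and their missing days to that date.
3. **Change the label.** Describe PDAOH of 100% as no death or hospital stay during observed follow-up, not as survival to study end.
4. **Add one sensitivity analysis** that puts patients who died and patients lost on the same time base to 1 May 2020. Use recovered vital status where available, and a stated assumption for the remaining unobserved time. Simply counting that time as alive should not be the only version, for the reason shown in the last step of the working.

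The cost is a few sentences in the SAP, one extra table and one extra analysis. A few weeks of survivor time after 1 May go unused. The cap uses a date the SAP already sets and needs no new data; only the sensitivity analysis benefits from further vital-status information.
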